8.3.13 Investigational product administration

For maximum 8 weeks from the next day of investigational product dispensing, 1 tablet/capsule will be administered orally once daily without regard to meals. Tablets/Capsules should be taken at a regular time, if possible. At each visit after the administration of the IP all subjects should return the unused IP prescribed at the previous visit and empty packaging.

8.3.14 Distribution and Collection of Subject Diary

The subject diary will be distributed at Visit 2 and the training on how to complete it will be provided. The completion status of the subject diary will be checked at Visit 3 via site visit, and appropriate training on the diary keeping will be performed, if necessary. At Visit 4, the completed subject diary will be collected and the subjects who have not symptoms relief will be prescribed the IP for Treatment 2 and the subject diary will be re-distributed to the subject. At Visit 5, the subject diary will be collected only from those who have undergone Treatment 2. Assessment of symptoms and treatment compliance will be done based on the subject diary

8.3.15 Adverse events

All adverse events occurring from administration of the IP until the end will be collected.

8.4 Efficacy Assessment

8.4.1 Efficacy Endpoints

8.4.1.1 Primary Efficacy Endpoint

Proportions of subjects with symptoms relief at week 4 measured by GERD-Q Score <8

8.4.1.2 Secondary Efficacy Endpoints

1. Proportions of subjects with symptoms relief at week 8 measured by GERD-Q Score <8
(Week 8 evaluation will only be applicable to patient receiving treatment 2)

2. Assessment on symptoms based on the diary of subjects

- The day to reach complete response (disappearance of heartburn, acid regurgitation, or heartburn/acid regurgitation for 7 consecutive days) after the first IP administration.
- Proportions of subjects without the major symptoms (heartburn, acid regurgitation, or heartburn/acid regurgitation) for first 7 days, 4 weeks, and 8 weeks after the first IP administration.
- Proportions of days free of major symptoms (heartburn, acid regurgitation, or heartburn/acid regurgitation) for first 7 days, 4 weeks, and 8 weeks after the first IP administration (including all daytime, nighttime, and daytime/nighttime)
- However, the secondary efficacy endpoints will only be assessed in patients who are not healed with treatment 1 and will continue to receive safety and rescue.

(Week 8 evaluation will only be applicable to patient receiving treatment 2)

3. Assessment on symptoms of reflux disease (GERD-Q)

- Changes from baseline in frequency by major symptom after 7 days, 4 weeks and 8 weeks.
(Week 8 evaluation will only be applicable to patient receiving treatment 2)

4. Assessment of Quality of Life (GERD-HRQL: GERD-Health related quality life)

- Changes from baseline in the total score of GERD-HRQL after 7 days, 4 weeks and 8 weeks.
(Week 8 evaluation will only be applicable to patient receiving treatment 2)

8.4.1.3 Exploratory Endpoints

Assessment on symptoms based on the diary of subjects.

- Proportions of subjects who have not been awakened during sleep for heartburn or acid regurgitation for first 3 days, 7 days, 4 weeks, and 8 weeks (or based on the day Investigator's need) after the first IP administration.

- Proportions of subjects who have relieved from chronic cough for first 3 days, 7 days, 4 weeks, and 8 weeks (or based on the day Investigator's need) after the first IP administration daytime and nighttime.
- Proportions of subjects who have relieved from irritating feeling in the throat for full 3 days, 7 days, 4 weeks, and 8 weeks (or based on the day Investigator's need) after the first IP administration daytime and nighttime.
(Week 8 evaluation will only be applicable to patient receiving treatment 2)

8.4.2 Method of Efficacy Assessment

8.4.2.1 Proportions of Subjects with Symptoms Relief

The proportions of subjects with symptoms relief at Week 4 after IP administration will be calculated. GERD symptoms relief is defined by GERD-Q Score <8

8.4.2.2 Assessment on symptoms based on the diary of subjects

The subjects will self-assess each symptom of 'heartburn' and 'acid regurgitation' (major symptoms of gastroesophageal reflux disease) twice daily (daytime/nighttime combined) in the subject diary which then will be collected and analyzed. In addition, the presence of 'chronic cough' and 'foreign body sensation in the throat' which are non-typical symptoms of gastroesophageal reflux disease will be assessed twice daily (daytime/nighttime combined), and any experience of awakening during sleep for heartburn or acid regurgitation will be collected.

The scale (0 to 4) for scores of assessing daytime/nighttime combined symptoms of 'heartburn' and 'acid regurgitation' is as follows:

Assessment on daytime symptoms		
0	None	No symptoms
1	Mild	Symptoms noticeable, but not bothersome
2	Moderate	A little bothersome and some limitations of daily activities
3	Severe	Symptoms noticeable for a lot of time and frequent limitations of daily activities
4	Very severe	Symptoms persistent and considerable limitations of daily activities

Assessment on nighttime symptoms		
0	None	No symptoms
1	Mild	Symptoms noticeable, but can be ignored, and do not disturb sleep
2	Moderate	A little bothersome and some disturbance of sleep
3	Severe	Symptoms noticeable for a lot of time and frequent disturbance of sleep
4	Very severe	Symptoms persistent and difficulties in sleeping

8.4.2.3 Quality of Life assessment (GERD-HRQL)

The subjects will self-assess their symptoms on the GERD-HRQL assessment sheet which then will be collected and analyzed. The subjects will rate from 0 to 5 for each question.

0	No symptoms
1	Symptoms noticeable, but not bothersome
2	Symptoms noticeable and bothersome, but not every day
3	Symptoms bothersome everyday
4	Symptoms affect daily activities
5	Symptoms are incapacitating to do daily activities

- **Total Score: Calculated by summing the individual scores to questions 1-15.**

- Greatest possible score (worst symptoms) = 75
- Lowest possible score (no symptoms) = 0

8.5 Safety Assessment

8.5.1 Safety Endpoints

1. Adverse events
2. Vital signs (blood pressure [diastolic/systolic], pulse rate, and body temperature)
3. Physical examination (head to toe general physical examination)
4. Laboratory tests (hematology, blood chemistry, blood coagulation, urinalysis, Liver function, Renal Function)

8.5.2 Adverse events

8.5.2.1 Definition of Adverse Events

An ‘adverse event (AE)’ is defined as any unfavorable and unintended sign (including abnormal laboratory test results), symptom or disease in a subject who received the IP and which does not necessarily have to have a causal relationship with this IP.

An ‘adverse drug reaction (ADR)’ is defined as any untoward and unintended response to the IP of any dose, of which causal relationship to the IP cannot be excluded.

A ‘serious adverse event (SAE)’ is defined as an untoward medical occurrence that at any dose of IP meets one or more of the following criteria.

- Results in death or is life-threatening
- Requires or prolongs hospitalization
- Causes permanent or significant disability or incapacity
- Results in congenital anomalies or defect
- Besides events above, occurrence of other medically important events such as drug dependence, drug abuse, or blood dyscrasias

However, the following hospitalization scenarios are not considered to be SAEs:

- Hospitalization/surgery scheduled prior to study participation
- For emergency room visit, ≤ 24 -hour stay in the emergency room (i.e., admission for > 24 hours is considered as an SAE)
- Hospitalization or prolongation of hospitalization for elective surgeries for diagnoses or existing diseases
- Hospitalization for purposes other than improvement/treatment of poor health conditions (e.g., respite care, caregiver on leave, administrative reason)

An ‘unexpected adverse drug reaction’ is one for which the nature or severity of the reaction is not consistent with the available product-related information including the Investigator’s Brochure.

8.5.2.2 Criteria and Method for Adverse Event Assessment

Confirmed information such as occurrence of adverse event (AE), AE term, severity of AE, date of onset and resolution, relationship to the investigational product, action taken, treatment, and outcome will be recorded on the case report form.

Any laboratory abnormality and abnormal finding in physical examination or vital signs that are considered clinically significant will be recorded as AEs.

Adverse event (AE) from the first IP administration to safety follow up visit (visit 4-1 or 5-1) must be recorded regardless of its relationship with the IP. At each visit after IP administration, the following methods may be done to identify AEs:

- Information provided by subject or legal guardian without any prompt
- At each visit, asking open-ended and non-suggestive questions
- Abnormalities observed by the investigator, other medical professionals and relatives.

Except for lost to follow-up, AEs (including AEs unresolved until the completion of the study) will be monitored, if possible, until the AEs recover to the pre-dose state or to the baseline, or the investigator determines that the AEs have normalized or further monitoring is unnecessary.

8.5.2.2.1 Severity of Adverse Events

The severity of adverse events (AEs) should be evaluated according to the following criteria.

- 1) Mild: An event that is easily tolerated by the subject, causing minimal discomfort and not interfering with normal daily activities (functions).
- 2) Moderate: An event that is sufficiently discomforting to interfere with normal daily activities (functions).
- 3) Severe: An event that prevents normal daily activities (functions).

8.5.2.2.2 Relationship to the Investigational Product

The investigator will determine the relationship between the adverse event (AE) and the IP in terms of subject's past history, health condition, treatment duration and treatment status.

1) Related: related or possibly related.

A) Certain

- The temporal sequence between the IP administration and the onset of the AE is reasonable.
- The AE is most plausibly explained by the administration of the product than any other causes.
- The AE disappears upon dechallenge.
- The result of rechallenge (performed if practically feasible) is positive.

- The AE shows a pattern consistent with the known information about the IP or other same-class drugs.

B) Probable/Likely

- There is evidence of the IP administration.
- The temporal sequence between the administration of the product and the onset of the AE is reasonable.
- The AE is more plausibly explained by the administration of the product than any other causes.
- The AE disappears upon dechallenge.

C) Possible

- There is evidence of the administration of the product.
- The AE follows a reasonable temporal sequence from the time of administration of the product.
- The AE is considered to have been caused by administration of the product, as much as by other possible causes.
- The AE disappears upon dechallenge (if performed).

D) Un-assessable

- There is some information available about the AE, but the relationship to the product cannot be assessed.

2) Unrelated (None): probably or definitely not related.

- The subject has not received the product, or
- The AE does not follow a reasonable temporal sequence from the time of administration of the product, or
- Other evident causes (use of other drugs, latent diseases, other factors, etc.) can provide a reasonable explanation for the AE

8.5.2.2.3 Action Taken for Investigational Product

- 1) Dose not changed
- 2) Dose interrupted
- 3) Permanently discontinued
- 4) Not applicable
- 5) Unknown

8.5.2.2.4 Treatments Provided for Adverse Events

- 1) Medication treatment performed for the adverse event
- 2) Non-medication treatment performed for the adverse event
- 3) Medication/non-medication treatment performed for the adverse event
- 4) Medication/non-medication treatment not performed for the adverse event

8.5.2.2.5 Outcome of Adverse Events

- 1) Recovered/Resolved
- 2) Recovering/Resolving
- 3) Not recovered/Not resolved
- 4) Recovered/Resolved with Sequelae
- 5) Death
- 6) Unknown

8.5.2.3 Handling and Compensation of Adverse Events

If AEs are experienced by subject, they should be reported to the Investigator. Addressing any adverse events or discomfort related to the study and providing appropriate treatment will be done by the Investigator. The Investigator will also remain vigilant about these adverse events. If severe adverse events are experienced, the Investigator may need to discontinue the treatment. The subjects will be informed of the best approach to manage adverse events.

Except for lost to follow-up, AEs (including AEs unresolved until the completion of the study) will be monitored, if possible, until the AEs recover to the pre-dose state or to the baseline, or the investigator determines that the AEs have normalized or further monitoring is unnecessary.

This study has been insured. The costs of medical treatment or reasonable compensation for research-related injuries resulting from adverse events in the study are provided by the sponsor in accordance with applicable local laws. Compensation will follow the sponsor's compensation guidelines. Costs covered by the subject's personal health insurance

will not be reimbursed by the sponsor.

8.5.2.4 Obligations and Reporting Methods of Responsible Person in Case of Serious Adverse Events

During the study, the principal investigator and the sub-investigator should ensure the safety of subjects and take actions quickly and appropriately to minimize adverse events. If “serious adverse drug reactions” occur during the study, the obligation and reporting method of each responsible person are as below.

1) Principal Investigator

In the event of any serious adverse event (SAE) during the study, the principal investigator should promptly contact to the sponsor and the CRO (the responsible monitor) via telephone or email within 24 hours of awareness and for any initial/follow-up SAE report the principal investigator should report within 3 calendar days to the IRB/EC. However, unexpected serious adverse drug reactions should be promptly reported to the sponsor and the IRB. In the event of reporting a death case, the principal investigator should provide additional information such as an autopsy report (only when performing an autopsy) and a death certificate to the sponsor and the IRB. The principal investigator should fully cooperate in providing the data and information of the report.

2) Sub-Investigators

Sub-investigators should report to the principal investigator and sponsor as soon as an SAE occurs during the study and make a further report on the details at a later time. However, unexpected serious adverse drug reactions should be promptly reported to the sponsor and the IRB.

3) Institutional Review Board/Ethical Committee

The Institutional Review Board (IRB)/Ethical Committee (EC) will ask the principal investigator to take necessary actions when any unexpected serious adverse drug reaction occurs or any new information that may adversely affect the safety of subjects or the conduct of the study becomes available.

4) Sponsor

The sponsor should periodically report additional safety information regarding the above report until the end of the AE (disappearance of the ADR or lost to follow-up) to the IRB/EC and/ or Indonesian Drug and Food Authority (BPOM) directly or through the CRO.

Safety Reporting Contact (within 24 hours of awareness)

TO CRO:

Telephone ([contact]
E-mail [contact]

TO SPONSOR:

Email 1 [contact]
E-mail 2 [contact]

8.5.3 Laboratory Tests, Vital Signs, Physical Examination

Results of the laboratory tests, vital signs, physical examination, will be evaluated for changes between before and after the IP administration and changes in normality/abnormality. Any clinically significant change will be recorded as an adverse event on the case report form.

8.5.4 Pregnancy

The subjects should use adequate methods of contraception during the study (Contraception should be maintained for at least 2 weeks from the last dose of IP). In this study, acceptable adequate methods of contraception for subjects or their partners:

- For Male subject: to use barrier method such as male condom and surgical sterilization such as vasectomy;
- For Female subject: to use 1) hormonal contraceptive such as Intrauterine system : intrauterine hormone-containing system, implant, injection, contraceptive pills, or 2) non hormonal contraceptive such as Intrauterine system : copper loop, barrier method : female condom, diaphragm or cervical cap, or surgical sterilization : tubectomy.

Female subject who became pregnant after enrolled to the study will be withdrawn from the study. The sponsor has the responsibility to follow up the outcome of the pregnancy in a female subject and male subjects' spouse (or partner) reported during the study. The information will be collected from the female subject and spouse (or partner) of male subject who have given a written consent to the informed consent form for collection of pregnancy information at the time the pregnancy is confirmed. Pregnancy itself will not be regarded as an adverse event unless the IP is suspected to have interfered with adequate methods of contraception or effects of contraceptives. Also, voluntary induced abortion without complications that is not a therapeutic abortion will not be considered as an adverse event and hospitalization for natural childbirth of a healthy baby will not be regarded as a serious adverse event.

Although pregnancy is not classified as a serious adverse event, the investigator should prepare a pregnancy report and report to the sponsor in the same way as serious adverse event reporting procedures in Section 8.5.2.4 within 24 hours of becoming aware of the pregnancy in a female subject or spouse (or partner) of a male subject. The investigator should follow and document the process and outcome of all pregnancy, even if the subject withdraws consent or terminates the study. Also, the investigator should prepare a pregnancy outcome report and report to the sponsor within 24 hours of becoming aware of any pregnancy outcomes (e.g., natural childbirth, spontaneous abortion). The follow-up of up to 7 days after delivery should be reported.

If an AE occurring during pregnancy meets the criteria for SAE (e.g., severe maternal complication, premature birth, therapeutic abortion, ectopic pregnancy, stillbirth, neonatal death, congenital anomaly, birth defect), it should be immediately reported to the sponsor according to serious adverse event reporting procedures in Section 8.5.2.4.

9 Data Analysis and Statistical Considerations

9.1 Analysis Sets

Per Protocol Set (PPS)

The PPS will include the subjects in the FAS who complete the study without any major protocol deviation. Major protocol deviations include 'violation of the inclusion and exclusion criteria', 'administration of prohibited concomitant medications during the study', etc. (see Section "13.5 Protocol Deviations"), and the subjects with other major deviations will be determined at the case report adjudication meeting prior to disclosure of randomization codes.

Full Analysis Set (FAS)

The FAS will include the subjects who receive the IP at least once after randomization and who have at least one efficacy assessment result. The subjects who violate the inclusion/exclusion criteria will be excluded from the FAS.

For the efficacy analysis, they will be included in the randomized treatment group regardless of the actual IP taken.

Safety Set

The safety set will include all the subjects who receive the IP at least once after randomization. The subjects who are enrolled in the study but withdrawn from the study before IP administration will be excluded from the safety set. For the safety analysis, the subjects will be analyzed according to the treatment they actually received.

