3.4 Criteria for Withdrawal

The subjects are allowed to spontaneously discontinue participation in this study at any time. The investigator may discontinue participation of a subject in this study at any time as per the subject's decision. However, a subject who are terminated early for showing a sufficient level of efficacy of the investigational product will not be considered as a withdrawal. If a subject is withdrawn from the study, the study results obtained from the discontinued/withdrawal case until the time point of discontinuation/withdrawal may be reviewed for evaluable items at the final evaluation.

In following cases, the investigator may withdraw the subject from the study.

- 1) Violation of inclusion/exclusion criteria is identified during the study.
- 2) Subjects are considered difficult to continue with the study due to adverse events as per the investigator's decision.
- 3) Subjects have received or are deemed to require medications or treatments that may affect the study results during treatment period or follow-up period.
- 4) Voluntary consent withdrawal by the subject or subject's legally acceptable representatives.
- 5) Subjects cannot not cooperate with the investigator.
- 6) Lost to follow-up.
- 7) The investigator decides to withdraw subjects.
- 8) Subject is pregnant during the study

If a subject determines to discontinue his/her participation and withdrawn from the study prior to completion, procedures scheduled for the Withdrawal visit should be performed. The procedure for the Withdrawal visit will be conducted within 2 weeks after the withdrawal decision is made. At the Withdrawal visit, the unused IPs or empty packaging will be returned, and the subject diary will be collected.

If the patient refused to visit, the vital sign, physical examination and lab test can be exclude. However, assessment of Gastroesophageal Reflux Disease Questionnaire (GERD-Q) and quality of life questionnaire (GERD-HRQL) must be performed at least by telephone call by the investigator, and all document should be written on the EMR by the investigator.s. To prevent any missing AEs that the investigator is not aware of, all kinds of methods must be employed to directly contact the subjects who refuse to visit such as phone call, letter, or personal visit. Any withdrawn subject cannot participate in the same study again.

4 Description of Study Design

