5.1 Scheduled Completion

If all protocol-specified procedures and assessments are completed after the IP administration, the subject will be considered to have completed the study. Subjects with symptoms relief at Week 4 measured by GERD-Q Score <8 will have the Safety F/U after 2 weeks from the date and be terminated from the study.

In this study, completion of the last subject is defined as the end of study.

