8.1 Visit Schedule

Subjects will provide written informed consent to participate in the study and then undergo any screening. Subjects who meet all of the inclusion criteria and none of the exclusion criteria based on the screening test results will be included into the study. Subjects will have a site visit 1 week after IP administration. Subjects will visit the study site again in person 4 weeks after the first IP administration to determine healing status with symptoms relief at Week 4 measured by GERD-Q Score <8 . Healed subjects will have a Safety F/U visit after 2 weeks (± 5 days) and unhealed subjects will take the IP for additional 4 weeks and then visit the site to determine healing status with symptoms relief at Week 8 measured by GERD-Q Score <8 . The Safety F/U visit will be conducted 2 weeks (± 5 days). The Safety F/U visit will be conducted via telephone visit and subjects will have a visit for additional tests or treatments based on the investigator's judgment.

In the event of withdrawal, the procedures for the Withdrawal visit will also be conducted by visiting the site within 2 weeks after the withdrawal decision is made. See Study Schedule Table for procedures to be performed at each visit.

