9.2 Statistical Analysis Method

9.2.1 General Principles of Result Analysis

The efficacy analysis will be conducted primarily on the PPS and FAS, and the PPS will be the primary analysis set.

In principle, all statistical analyses will use SAS® version 9.4 or higher and be performed with a two-sided test at a significance level of 5%, unless otherwise specified.

Descriptive statistics (mean, standard deviation, median, minimum, and maximum) will be calculated and provided for continuous variables, and the frequency and percentage will be provided for categorical variables.

The last observation carried forward (LOCF) method will be applied for correction of missing data of continuous endpoints among efficacy endpoints, and if the LOCF method cannot be applied, the raw data will be analyzed without correcting the missing data. However, the quality-of-life score (GERD-HRQL) will be analyzed using the raw data without applying the LOCF. For survival analysis, censoring will be utilized. When applying the LOCF, if the value immediately before the missing value is the baseline value, it will not be replaced.

The missing values of efficacy endpoints will be handled for both analyses on the FAS and PPS, and the safety endpoints will be analyzed with the raw data without replacing the missing values.

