13.5 Protocol Deviation

If any protocol deviation becomes known during the study, the investigator should notify the deviation to the sponsor as soon as possible and decide whether to continue participation of the subject in the study. The followings are regarded as major protocol deviations:

- 1) Violation of inclusion and exclusion criteria
- 2) Administration of prohibited concomitant medications/therapies that may affect the study results
- 3) Treatment compliance of <80% or >120%
(Treatment compliance refers to the mean treatment compliance throughout the study treatment period for Fexuprazan 40 mg).
- 4) Other deviation considered as a major protocol deviation

For other minor deviations, the degree and reason of deviation or delay will be described accurately, and consideration on whether the study has been affected will be made at the time of result analysis.

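### The Week-4 primary analysis set is tied to study completion, so events in Weeks 5–8 can remove known Week-4 failures; successes have a much shorter exposure, and the FAS need not agree

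*Combined protocol and SAP*

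**What the plan says.** Section 9.1 defines the primary set: "The PPS will include the subjects in the FAS who complete the study without any major protocol deviation". Section 9.2.1 gives its status: "The efficacy analysis will be conducted primarily on the PPS and FAS, and the PPS will be the primary analysis set". The FAS in Section 9.1 needs one dose and one efficacy result, excludes eligibility violators, and has no completion requirement.

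Section 5.1 defines completion: "If all protocol-specified procedures and assessments are completed after the IP administration, the subject will be considered to have completed the study". The route then depends on the Week-4 result:

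- **Relieved at Week 4 (Section 5.1):** these subjects "will have the Safety F/U after 2 weeks from the date and be terminated from the study". Section 8.1 makes that follow-up a telephone contact.
- **Not relieved at Week 4 (Section 8.1):** "unhealed subjects will take the IP for additional 4 weeks and then visit the site". The two-week follow-up comes after that.

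Under Section 3.4, a subject "terminated early for showing a sufficient level of efficacy of the investigational product will not be considered as a withdrawal". Section 13.5 counts prohibited medication and compliance below 80% or above 120% as major deviations, and adds: "Treatment compliance refers to the mean treatment compliance throughout the study treatment period for Fexuprazan 40 mg".

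The decision rule in Sections 9.2.3.1 and 9.3 is a lower 95% limit above -0.1. It names no analysis set. Nothing limits PPS completion or deviations to the first four weeks for the Week-4 endpoint.

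**The concern.** Membership of the primary set depends on what happens after the primary outcome has been recorded, and the length of that exposure depends on the outcome itself. Failures face four more weeks of treatment, a site visit and a follow-up call. Successes face the call and the two weeks before it. Three kinds of event in Weeks 5–8 can remove a failure: withdrawal, prohibited medication, and mean compliance pulled below 80%. Subjects with persisting symptoms are plausibly the ones most likely to leave or to take other treatment. The trial is open-label, so those decisions can also depend on the known drug.

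Losing failures raises the relief rate in each arm. If the loss is similar in both arms, a true deficit moves towards zero, which favours a non-inferiority claim. The usual argument that a per-protocol set is the cautious choice for non-inferiority cannot then be relied on. What is at stake is the trial's only confirmatory conclusion.

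**Working it through.** **1. The plan's own figure.** Section 9.4.2 gives control 88.5%, study drug 94.0%, margin -0.1, one-sided 2.5% and a pooled-variance Z-test.

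- Mean rate = (0.885 + 0.940)/2 = 0.9125.
- Pooled SE = √(2 × 0.9125 × 0.0875/53) = 0.05489.
- Unpooled SE = √((0.885 × 0.115 + 0.940 × 0.060)/53) = 0.05463.
- Power = Φ((0.155 - 1.96 × 0.05489)/0.05463) = Φ(0.868) = 0.807, matching the stated 0.80729.
- Dropout: 53/0.8 = 66.25, rounded up to 67 per group, 134 in total. This reproduces.

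**2. Selection formula.** Let p be the true Week-4 relief rate, d the share of failures lost from the PPS, and s the share of successes lost. The rate in the PPS is

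q = p(1 - s) / [p(1 - s) + (1 - p)(1 - d)].

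The documents give no value for d or s; both are assumptions.

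Example at the margin (fexuprazan 78.5%, control 88.5%) with d = 20% in both arms and s = 0:

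- Fexuprazan: 0.785/(0.785 + 0.215 × 0.8) = 0.8203.
- Control: 0.885/(0.885 + 0.115 × 0.8) = 0.9058.
- Difference: -8.6 points instead of -10.

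**3. False-claim rate.** Exact binomial enumeration with 53 analysed per arm; a claim is made when the lower 95% Miettinen–Nurminen (score) limit exceeds -0.1. The score interval is also an assumption, because Section 9.2.3.1 names only the chi-square or Fisher's exact method.

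| Failures lost, fexuprazan / control | Successes lost (each arm) | Expected PPS difference (points) | False-claim rate |
|---|---|---|---|
| 0% / 0% | 0% | -10.0 | 2.5% |
| 10% / 10% | 0% | -9.3 | 3.1% |
| 20% / 20% | 0% | -8.6 | 4.0% |
| 40% / 40% | 0% | -6.9 | 6.9% |
| 40% / 20% | 0% | -4.7 | 12.5% |
| 20% / 40% | 0% | -10.7 | 1.9% |
| 20% / 20% | 10% | -9.2 | 3.2% |

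**4. Sensitivity to method.** A simulation of 400,000 trials started from 53 per arm at Week 4 and removed failures from that number. At 20%/20% it gave 3.9% with a Newcombe limit and 5.0% with a Wald limit, against 2.5% and 3.1% with no loss.

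**5. How few subjects this takes.** With 53 per arm at the margin, about 53 × 0.215 = 11.4 fexuprazan and 53 × 0.115 = 6.1 control failures are expected. A 20% loss is about two and one subjects. At the planning rates, expected failures are only 53 × 0.060 = 3.2 and 6.1. There, 20% equal loss barely changes the chance of a claim (Newcombe 77.4% to 76.9%; Wald 82.5% to 84.2%). The cost falls mainly where the drug is truly worse.

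**6. The withdrawal rule.** Section 9.2.3.1 uses the final observation, including the Withdrawal visit. Withdrawn subjects are not completers, so their Withdrawal-visit results can count only in the FAS.

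**The case against.** A reader might infer three stronger things that the documents do not support.

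- **That the claim rests on the PPS alone.** Section 9.2.1 also specifies an FAS analysis, which keeps these failures and would show a discrepancy. What stands is narrower: the PPS is designated primary and agreement is not required.
- **That no Week-4 success can be lost after Week 4.** A success still has the two-week follow-up. Section 3.4 allows withdrawal for medication during follow-up, and Section 9.1 counts prohibited medication at any time in the study. The exposure is shorter, not zero. Allowing for 10% of successes lost brings the 20%/20% case down from 4.0% to 3.2%.
- **That the bias always favours fexuprazan.** It does so if loss is equal or heavier on fexuprazan. If control failures are lost sufficiently more often, the test becomes stricter, as the 1.9% result shows.

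The loss rates are also hypothetical. The only attrition figure is 20% overall in Section 9.4.2, which includes losses before Week 4; 40% of failures is twice that.

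Compliance averaging can work the other way too. A failure at 75% in Weeks 1–4 and 95% in Weeks 5–8 averages 85% and stays in, whereas a success at 75% over four weeks is excluded. Section 13.5 words the compliance definition for fexuprazan only, so its application to the control arm is unclear.

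Loss of subjects who withdraw before Visit 4 is ordinary for a per-protocol set and is not evidence of this asymmetry.

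These points limit the size and direction of the effect. They do not remove the fact that post-outcome events decide whether a known Week-4 result counts.

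**Conclusion.** The concern holds in a conditional form. Read literally, the plan lets events in Weeks 5–8 delete known Week-4 failures from the primary Week-4 comparison, with a much shorter equivalent exposure for successes and no requirement that the FAS agree. Under equal loss of 10% to 40% of failures and no loss of successes, the one-sided false-claim rate is 3.1% to 6.9% instead of 2.5%. Unequal loss can take it to 12.5% or down to 1.9%. All of these rest on assumed loss rates, true rates exactly at the margin, 53 analysed per arm and a score interval. Because the effect depends on losses that may not occur, and a specified FAS analysis would help to expose it, this is a should-fix point.

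**What to change.** For the Week-4 endpoint, define the PPS on Day 0 to Visit 4 only: Visit 4 GERD-Q available, and compliance and major deviations assessed up to Visit 4, whatever happens in Treatment 2. State that the compliance criterion applies to both arms. A separate definition can serve the Week-8 analyses.

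Add to Sections 9.2.3.1 and 9.3 that non-inferiority is concluded only if the lower limit exceeds -0.1 in both the PPS and the FAS. This second condition is needed because subjects who leave before Visit 4 still drop out of the revised PPS.

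The synopsis treats a GERD-Q score above 8 as non-healed, while relief is a score below 8. These must be reconciled so that the completion route for a score of exactly 8 is defined.

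The cost is a wording amendment before database lock. The planned 53 per group and 134 in total stand. Requiring both sets slightly lowers the chance of a positive claim.
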